12.5 Subject Compliance

Study drug compliance will be assessed by the investigator and/or study center staff by recording capsule counts of study treatments from the previously dispensed capsules, separately for "Morning" and "Evening" bottles. The investigator and/or study center staff will also assess whether the subject has been given the capsules in the prescribed order. The total number of doses administered to each subject will be derived from dosing information recorded in the eCRF.

Caregivers must bring the bottles back at each study center visit. Any remaining capsules will be counted and recorded to assess compliance. Caregivers shall be questioned as to the reason why remaining capsules have not been administered (e.g. forgot because not part of routine, subject refused, subject had side effects so parent decided to give a drug holiday, couldn't open the bottle, down-titration recommended by doctor, etc.) and the approximate time of any missed doses.

12.6 Study Drug Accountability

Records shall be maintained of the delivery of study drugs to the study centers, the inventory at the study centers, the use by each subject and the return to Ovid Therapeutics Inc.

These records shall include dates, quantities, batch numbers, expiry dates and the unique code numbers assigned to the study drug and to the study subjects.

The investigator shall be responsible for ensuring that the records adequately document that the subjects were provided the doses specified in the protocol and that all study drug received from Ovid Therapeutics Inc. is reconciled. All randomization codes must be returned to Ovid Therapeutics Inc. at the end of the study.

After completion of the study, all unused study drug will be inventoried and returned to Ovid Therapeutics Inc. or as directed by them.

12.7 Concomitant Therapy

Medication other than those listed in the Exclusion Criteria (Section 11.3) that are given at stable dose for at least 4 weeks prior to Baseline (e.g. constant use of sleep or anti-epileptic medication) are acceptable, and must be documented in the eCRF.

Any changes in dose should be avoided during the study and, if felt necessary, be previously discussed with the Medical Monitor.

Medications that are not prohibited and considered necessary for the subject's safety and well-being may be given during the study at the discretion of the investigator and must be recorded in the appropriate sections of the eCRF.

All prior medications taken within 30 days and ongoing concomitant medication must be documented in the eCRF.

Subjects must be receiving a stable dose of concomitant medications, including anti-epileptic medication, gabapentin, clonidine, melatonin, trazadone, supplements, and special diets, for at least 4 weeks prior to Baseline, and be able to maintain these throughout the study. Modifications may be made per investigator judgment based on urgent need or medical necessity. Subjects with questions about allowed concomitant therapy should seek medical guidance from the investigator.

13. DISCONTINUATION OF STUDY TREATMENT OR WITHDRAWAL OF SUBJECTS FROM STUDY

13.1 Withdrawal/Discontinuation of Individual Subjects

The reasons for study drug discontinuation and/or subject withdrawal from the study must be recorded in the subject's eCRF. The investigator must notify Ovid Therapeutics Inc. and/or the Medical Monitor immediately when a subject has been discontinued/withdrawn due to an AE.

13.1.1 Withdrawal from the Study

Subjects or their caregiver may withdraw subjects from the study at any time for any reason without compromising the subject's medical care. The investigator may also withdraw subjects from the study.

Subjects who withdraw from the study prior to the End of Treatment visit should complete the procedures scheduled for that visit. The reason for subject withdrawal will be recorded in the eCRF.

Withdrawal of subjects for any reason should be discussed with the Medical Monitor.

13.1.2 Discontinuation of Study Drug

If it is necessary to discontinue the study drug earlier than planned, subjects should continue to be followed per protocol to capture safety and efficacy assessments for the duration of the study period if feasible.

The investigator may withdraw the subject from the study drug for the following reasons:

- Upon subject's or caregiver's request
- The subject or caregiver is unwilling or unable to adhere to the protocol-specified visits
- The subject experiences an intolerable AE
- During the study, the subject develops symptoms or conditions listed in the exclusion criteria
- Other medical reason, at the discretion of the investigator and/or the Medical Monitor

Subjects who discontinue the study due to an AE considered related to study drug should be followed until the event is resolved, considered stable, or the investigator determines the event is no longer clinically significant. Study drug discontinuation due to AEs considered not related to study drug will be followed until resolution.

13.2 Study Termination

The study, or any portion of it, may be terminated at any time for safety reasons including the occurrence of AEs or other findings suggesting unacceptable risk to subjects, administrative, or operational reasons. Study centers must promptly notify their IRB and initiate withdrawal procedures for participating subjects.

14.

14.1 Efficacy Assessments

A large black rectangular redaction box covers the majority of the page content, from approximately y=113 to y=886. The redaction is positioned in the upper half of the page, with the rest of the page being white space.

A large block of text that has been completely redacted with black bars. The redaction is not uniform, with some lines being completely covered and others showing through as white space. The pattern of redaction is irregular, suggesting a manual or hasty process.

A series of horizontal black bars of varying lengths, with the longest bar positioned in the center. This visual element is likely a placeholder or a decorative graphic in the document.

| Term | Percentage |
|------------|------------|
| GMOs | 85% |
| Organic | 75% |
| Natural | 70% |
| Artificial | 65% |
| Organic | 60% |
| Natural | 55% |
| Artificial | 50% |
| Organic | 45% |
| Natural | 40% |
| Artificial | 35% |

[figure not shown]
[figure not shown]
14.1.4 (Mal)adaptive Behaviors:

- The **Aberrant Behavior Checklist - Community (ABC-C)** is a rating scale that measures the severity of a range of problem behaviors commonly observed in individuals with intellectual and developmental disabilities¹⁷. It is completed by the caregiver. It is an empirically developed scale designed to measure psychiatric symptoms and behavioral disturbance exhibited by individuals across 5 domains with 58 items: irritability, agitation, and crying (15 items), lethargy, social withdrawal (16 items), stereotypy (7 items), hyperactivity/noncompliance (16 items), and inappropriate speech (4 items). Most individuals with AS are not able to communicate thoughts of suicidality, so subject irritability reported by the caregiver is being used as a surrogate measure of suicidality.
 - The ABC-C Irritability subscale will be used as an indicator for suicidality. The investigator will review the scale items with the caregiver at each scheduled time point. If grading worsens, the investigator must decide whether that indicates a suicidal ideation of the subject, and if so, must document it as an AE and closely monitor it until resolution. The ABC-C Irritability subscale will be used to assess risks of suicidality (safety variable). The Aberrant Behavior Checklist was developed for use with individuals living in institutions and residential settings. Revisions to the measure have made it more applicable for home and school settings; the commonly used measure is now the ABC-C version.

A decorative horizontal bar consisting of a thick black line with a series of smaller black squares and rectangles of varying sizes extending from its right side. The pattern is irregular and suggests a sense of motion or a stylized architectural element.

14.1.5 Clinical Change:

Clinical Global Impressions (Severity [CGI-S] and Improvement [CGI-I] scales). Both scales will assess all sub-domains of AS (gross and fine motor ability, sleep, and adaptive behavior) and will be filled out by the caregiver and investigator. For the CGI-S, the rating should be relative to all people, including typically developing individuals in the community. This rating is based upon observed and reported symptoms, behavior, and function. The CGI-I rates total improvement compared to the subject's condition at baseline.

15. SAFETY ASSESSMENTS

Details for safety assessments are provided below. Details regarding the management of AEs are provided in Section 16.

15.1 Suicidality

Most individuals with AS are not able to communicate thoughts of suicidality, so subject irritability reported by the caregiver is being used as a surrogate measure of suicidality. The ABC-C Irritability subscale will be used as an indicator for suicidality. The investigator will review the scale items with the caregiver at each scheduled time point. If grading worsens, the investigator must decide whether that indicates a suicidal ideation of the subject, and if so, must document it as an AE and closely monitor it until resolution.

15.2 Physical Examination

A physical examination should be performed at each visit to evaluate the medical condition of the subject and detect any sign/symptom of AEs, and to perform all the procedures required per protocol.

A full physical examination will include a relevant general assessment of: head, eyes, ears, nose and throat; neck; heart; chest (including lungs); abdomen; extremities; skin; lymph nodes; as well as neurological and cardiovascular systems.

15.3 Vital Signs

The following vital signs will be recorded during this study (this must include but not be limited to the measurement of changes in heart rate and blood pressure):

- Heart rate
- Blood pressure
- Body temperature
- Weight

15.4 Laboratory Assessments

Blood samples will be collected for routine clinical laboratory safety evaluations. Study center staff can apply the best local practices to obtain a blood sample in this population.

Additional laboratory safety evaluations will be performed at other times, if judged to be clinically appropriate, or if the ongoing review of the data suggests a more detailed assessment of laboratory safety evaluations is required. Any changes to the scheduled times of laboratory safety tests will be agreed with [REDACTED] and Ovid Therapeutics Inc. and documented. The investigator will perform a clinical assessment of all laboratory safety data.

Laboratory parameters include electrolytes, lipids, glucose, renal, hepatic and pancreatic function tests, and hematology. A serum pregnancy test will be done for female subjects at the times noted in Table 1.

Table 3 lists the clinical chemistry and hematology tests planned for this study.

Table 3 Clinical Chemistry and Hematology Tests

| Clinical Chemistry | Hematology |
|---|------------------------|
| Albumin | Basophils (absolute) |
| Alkaline phosphatase | Eosinophils (absolute) |
| Alanine aminotransferase | Lymphocytes (absolute) |
| Aspartate aminotransferase | Monocytes (absolute) |
| Bicarbonate | Neutrophils (absolute) |
| Calcium | Basophils |
| Chloride | Eosinophils |
| Cholesterol | Hematocrit |
| Creatine kinase | Hematology slide |
| Creatine, enzymatic | Hemoglobin |
| Direct bilirubin | Lymphocytes |
| Glucose, random, serum | Monocytes |
| High density lipoprotein cholesterol | Neutrophils |
| Indirect bilirubin | Platelets |
| Lactate dehydrogenase | Red blood cells |
| Low density lipoprotein cholesterol, calculated | White blood cells |
| Phosphorous | - |
| Potassium | - |
| Sodium | - |
| Total bilirubin | - |
| Total protein | - |
| Triglyceride | - |
| Urea (blood urea nitrogen) | - |
| Uric acid | - |
| Total cholesterol | - |
| Magnesium | - |
| Thyroid stimulating hormone | - |

15.5 Electroencephalogram Assessments

EEG will be assessed as changes in background rhythms and the frequency of epileptiform discharges. Study centers will perform a routine EEG with local equipment. EEG should be done towards the end of a visit to minimize any confounding impact on subject performance. Standard protocol and montage will be followed as outlined in the separate EEG manual, including but not limited to resting and evoked stimuli. Placing of electrodes (if possible according to the international 10/20 system) must be documented. Recording should last about 10 minutes in the wake state, and if possible, recording should end with a nap period. Data will be collected in electronic format in European Data Format for centralized reading. An EEG manual will be provided.

15.6 Optional Biomarker Analysis

Additional biomarker samples will be acquired from all subjects for whom the caregiver provides separate informed consent for purification of DNA, and plasma, to allow for identification of secondary pathogenic variants and metabolic profiles.

Two tubes of blood will be collected at baseline for biomarker plasma and biomarker DNA and one tube of blood will be collected at End of Treatment (Day 84) for isolation biomarker plasma. DNA will be used to identify secondary pathogenic variants that may be present (e.g. microdeletions encompassing 2q21.3)¹⁸ and plasma for quantification of metabolites (e.g. glutamic acid)¹⁹. This data will not be captured in the CSR.

16. SAFETY DEFINITIONS, RECORDING, REPORTING, AND RESPONSIBILITIES

The timing and frequency of safety assessments are described in Table 1 and Section 15.

16.1 Adverse Events

16.1.1 Definitions

The definitions for TEAEs, AEs, and SAEs are given below. The Principal Investigator is responsible for ensuring that all study center staff are familiar with the content of this section. Any AE experienced by the subject between the screening visit (Day -28) and up to completion of the follow-up period after the last administration of study drug (Day 98 follow-up phone visit) must be recorded on the eCRF, regardless of the severity of the event or its relationship to study treatment.

Adverse Event (AE)

An AE is defined as any untoward medical occurrence in a clinical investigation subject, administered a pharmaceutical product, and which does not necessarily have a causal relationship with this treatment. An AE can therefore be any unfavorable and unintended sign (including an abnormal laboratory finding), symptom or disease temporally associated with the use of a medicinal (investigational) product, whether or not related to the medicinal (investigational) product.

Determination of whether an abnormal laboratory value meets the definition of an AE will be made by the investigator. Although abnormal laboratory values are typically not considered AEs, the following considerations may result in an abnormal laboratory value being considered an AE:

- A laboratory test result meets the criteria for an SAE
- A laboratory test result requires the subjects to receive specific corrective therapy
- A laboratory abnormality that the investigator considers to be clinically significant

Any intolerance that triggers a dose reduction during the titration period must be documented as an AE.

Treatment-Emergent Adverse Event (TEAE)

A treatment-emergent adverse event (TEAE) is defined as an AE with an onset that occurs after receiving study drug (AE start date \geq first dose date) and within 30 days after receiving the last dose of study drug (AE start date minus last dose date \leq 30), or an AE that occurs pre-treatment but worsens post treatment.

Serious Adverse Event (SAE)

An SAE is any untoward medical occurrence that at any dose:

- Results in death

- In the view of the investigator, places the subject at immediate risk of death (a life-threatening event); however, this does not include an event that, had it occurred in a more severe form, might have caused death
- Requires inpatient hospitalization or prolongs existing hospitalization. Planned hospitalizations will NOT be reported as an SAE unless categorized as otherwise medically important
- Results in persistent or significant disability/incapacity
- Is a congenital anomaly/birth defect
- Is otherwise medically important: Important medical events that may not result in death, be life-threatening or require hospitalization may be considered a serious adverse drug experience, when based on appropriate medical judgment, they may jeopardize the subject or the subject may require medical or surgical intervention to prevent one of the outcomes listed in this definition

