3.9.1 Adverse Events

All adverse events will be coded using the Medical Dictionary of Regulatory Activities (MedDRA) Version 19.1 and will be classified by MedDRA system organ class (SOC), high level group term (HLGT), high level term (HLT), and preferred term (PT). Analyses of adverse events will be performed using the Safety Analysis Set.

Treatment emergent adverse events (TEAEs) are any adverse events occurring or worsening in severity after the first administration of study medication. The following imputation rules will be used for missing or incomplete AE start dates:

- Missing AE start day:
 - If the partial date contains a different month from the date of first study dose, then impute it as the first day of the month.
 - If it contains the same month as the date of first dose, then impute it as date of first dose.
- Missing AE start day and month:
 - If the partial date contains a different year from the date of first dose, then impute the missing day and month as Dec 31.
 - If it contains the same year as the date of first dose, then impute the missing day and month as day and month of first dose.
- Completely missing AE date:
 - Impute the missing date as the date of first dose.

The TEAE incidence will be presented by treatment group for all subjects in the Safety Analysis Set. The number and percentage of subjects who experience at least one TEAE and the number and percentage of subjects who experience at least one TEAE within each specific SOC and PT will be presented by treatment group (placebo, combined OV101 and separate dose groups). Additionally, the incidence of TEAE within each specific SOC, HLGT, and PT and specific SOC, HLT, and PT will be presented. The 95% CIs will be displayed for the frequency of TEAEs. Treatment-related AEs will be considered those at least possibly related to investigational product based on the investigator's assessment. The number and percentage of subjects reporting serious AEs, treatment-related AEs, and AEs leading to treatment discontinuation will also be summarized for each treatment group by MedDRA SOC and PT.

The AEs of Special Interest include Dizziness, Somnolence, Nausea, Vomiting PTs, and will be reported separately.

All adverse event data including baseline adverse events will be displayed in subject data listings.

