10.1.3.2 Treatment Period (12 Weeks)

Baseline Visit (Day 1; Full Day Visit)

Eligible subjects will return to the study center for the Baseline (Day 1) visit. Caregivers will bring the e-Diary and wearables. Prior to randomization, study center staff must confirm proper recording of the wearables, appropriate completion of the e-Diary, and fulfillment of all selection criteria.

Subjects will be randomized on a 1:1:1 ratio according to the following dosing schedule:

- Schedule A: a single evening dose of OV101 (QD) plus morning placebo
- Schedule B: a morning plus evening dose of OV101 (BID)
- Schedule C: morning and evening placebo

- Subjects will receive the assigned package of blinded study treatment as per treatment code for the titration period and until the next scheduled visit at Week 6
- Baseline safety and efficacy assessments will be conducted

- Baseline laboratory assessments will be performed

The e-Diary will be kept by the caregiver throughout the study. It must be charged overnight each day by the caregiver. Study center staff shall remotely check data completeness at least once a week and contact caregiver if there is non-adherence, such as missing data.

Titration (Day 1 to Day 14)

Section 12.1.1 details the dosing schedule.

During the titration period (Day 1 to Day 14), doses progressively increase in 5 mg increments according to the titration schedule, allowing slower up- or down-titration if the OV101 or placebo treatment is not tolerated (Table 2) up to a target evening dose of 15 mg (3 capsules) in Schedules A and B, and up to a target morning dose of 10 mg (2 capsules) in Schedule B. Multiple phone visits are scheduled to confirm tolerability of study treatment. Each dose-escalation will be performed after adequate tolerability has been assessed by the caregiver and investigator during a phone visit. At any time, ad-hoc study center visits may occur to further assess drug safety. These should follow the script for phone visits.

If the target dose is not achieved at Day 14 (due to slowed titration based on intolerance), the up-titration can continue until the target dose or the maximum tolerated dose is reached. Additional phone visits to agree on next titration level will be performed. As a general guidance for investigators, for subjects undergoing a slowed titration regimen, the maximal tolerated dose for the duration of the study should be reached by Day 21.

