12.1.3 Administration of Study Treatments

OV101 will be supplied as a 5 mg capsule, and matching placebo, in bottles. The caregiver will receive a sufficient number of capsules in 1 bottle "Morning" and 1 bottle "Evening" at the baseline visit and at the Week 6 interim visit.

All subjects will receive a morning dose of OV101 or placebo and an evening dose of OV101 or placebo during the entire duration of treatment. Two dosing schedules of OV101 will be assessed; a single evening dose (Schedule A: QD) based on what was previously clinically assessed in the treatment of sleep disorder, and a morning plus evening dose (Schedule B: BID) designed to provide a more sustained exposure. Schedule C is morning and evening placebo (BID). All subjects will be up-titrated to the target dose unless this target dose is not tolerated (for titration conventions see below). All subjects will receive treatment for a maximum of 12 weeks at their highest tolerated dose. The last dose of study drug should be taken the morning of the Day 84 visit if the subject is on the BID dosing regimen.

Given the potential effects with food previously described:

- For the morning dose, it is recommended that the study drug be given with or shortly after the morning meal
- For the evening dose, it is recommended that study drug be given within 30 minutes of scheduled bedtime

The capsules can be opened and content added to one spoon of semi-liquid food (applesauce, pudding etc.). CAPSULE CONTENT CANNOT BE PLACED IN LIQUID. It must be documented specifically how the capsules were taken e.g. swallowed whole or taken in one spoon of applesauce or other food.

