12.1.3.3 Titration Initiation

Day 1: Treatment can start on any day during the week. The next up-titration will occur on Day 3. If the defined interval occurs during the weekend, a +2 day window for next titration step is acceptable, but the investigator should consider scheduling the start of treatment appropriately to limit titration steps occurring during the weekend. All subjects will start with 1 capsule (OV101 or placebo) in the evening.

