16.1.1.6 Reporting of Serious Adverse Events

Investigators and other study center staff must inform appropriate [REDACTED] representatives of any SAE that occurs (whether or not attributable to the study drug) in the study within 24 hours (i.e. immediately but no later than the end of the next business day) or when he

or she becomes aware of it. It is the investigator's responsibility to ensure that SAE reporting procedures are followed appropriately.

All SAE reports must be faxed to the following number within 24 hours:

[REDACTED]
[REDACTED]
[REDACTED] [REDACTED]
[REDACTED] [REDACTED]
[REDACTED]
[REDACTED]
[REDACTED] [REDACTED]
[REDACTED] [REDACTED]
[REDACTED] [REDACTED]
[REDACTED]

In a study-related medical emergency situation, when assigned Medical Monitors for a study cannot be reached by a caller, an on-call Physician can be reached 24 hours per day, 7 days per week via the [REDACTED]

[REDACTED] [REDACTED]

(chargeable telephone number allowing a global reach from both landlines and mobile phones)

[REDACTED]

On this internet page, a list of country-specific toll-free telephone numbers is provided. It should be noted that not all countries globally have access to toll-free numbers as indicated on the "24/7 Medical Help Desk" index. Countries without toll-free numbers need to dial the chargeable number as indicated above. Furthermore, toll-free numbers are not available from mobile phones.

The [REDACTED] will work with the investigator to compile all the necessary information and ensure that the appropriate Ovid Therapeutics Inc. representative receives a report within one day (24 hours) for all fatal and life-threatening cases and within 5 days for all other SAEs.

Follow-up information on SAEs must also be reported by the investigator within the same time frames.

If a non-serious AE becomes serious, this and other relevant follow-up information must also be provided to [REDACTED] within one day as described above. For a non-serious AE that become serious but which is not fatal or life-threatening a report should be received within 5 days.

The following variables will be recorded for each AE: verbatim/AE description, time and date for AE start and stop, maximum intensity, seriousness, causality rating, whether or not the AE caused the subject to discontinue, and the outcome.

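### The protocol's date-only TEAE rule counts Day 1 events that start before the evening first dose, against its own wording and the SAP's; neither document gives a same-day rule

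*Combined protocol and SAP*

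**What the plan says.** Protocol section 16.1.1 opens the TEAE window with "onset that occurs after receiving study drug (AE start date \geq first dose date"). It closes the window in the same date-based way, "within 30 days after receiving the last dose of study drug (AE start date minus last dose date \leq 30"), and adds pre-treatment events that worsen after treatment. SAP section 3.9.1 defines TEAEs as "any adverse events occurring or worsening in severity after the first administration of study medication". It does not repeat the date comparison and gives no clock-time rule. Its imputation rules concern incomplete start dates; for a missing day they state: "If it contains the same month as the date of first dose, then impute it as date of first dose".

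The timing of Day 1 comes from the protocol:

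- Section 10.1.3.2 heads the visit "Baseline Visit (Day 1; Full Day Visit").
- Section 12.1.3.3 says "All subjects will start with 1 capsule (OV101 or placebo) in the evening".
- Section 12.1.3 adds that for the evening dose "it is recommended that study drug be given within 30 minutes of scheduled bedtime".

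Table 1 schedules AE collection at Baseline, and section 16.1.1.2 has AEs recorded from screening onward. Section 16.1.1.6 lists the variables kept for each AE, among them "time and date for AE start and stop, maximum intensity". The synopsis names TEAE incidence as the primary endpoint.

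**The concern.** A date-only rule matches its wording only if nothing can begin on the first-dose date before the dose. Here most of a day can pass first, and it is spent in a clinic visit with safety and efficacy assessments and an EEG. An event that starts during that visit satisfies the bracket in protocol section 16.1.1 but not the words in front of it, and not the SAP's definition.

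At stake is whether the primary endpoint can be reproduced. Two competent programmers, one working from the protocol and the other from the SAP, could produce different TEAE counts from the same data. The affected events would be ones that no study drug could have caused.

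**Working it through.** **1. The plan's own figure.** Protocol section 17.1 rests the sample size on the precision of AE rates. The half-width is 1.96 × √[p(1 − p)/n] with p = 0.25.

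- n = 25: 1.96 × √(0.1875/25) = 0.1697, stated as 17%.
- n = 20: 1.96 × √(0.1875/20) = 0.1898, stated as 19%.

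Both reproduce. This point does not dispute them, and the fix leaves the planned figures unchanged.

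**2. The possible codings.** Take a first dose at 20:30 on Day 1 and two complete AE records from that day. The clock times are illustrative.

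| Coding | AE at 11:00 (before dose) | AE at 21:30 (after dose) |
|---|---|---|
| Start date ≥ first-dose date (protocol bracket) | TEAE | TEAE |
| Start date > first-dose date (one literal date reading of 'after') | not a TEAE | not a TEAE |
| Start date-time ≥ first-dose date-time | not a TEAE | TEAE |

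Only the third row matches the words of both documents. The second row matters as well. Protocol section 8.1 reports that most AEs in earlier work came on within 1 to 2 hours of dosing, so a strict later-date rule would lose genuine first-night reactions.

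**3. Weight of one subject.** 1/25 = 4 percentage points of incidence in an arm of 25, or 1/20 = 5 points at the protocol's minimum arm size.

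**4. Illustrative size.** Let q be the share of subjects with an AE starting on Day 1 before the dose. The documents give no value for q, so the range below is assumed. If such events are independent of later ones, the incidence under the date rule is p′ = 1 − (1 − p)(1 − q) = p + (1 − p)q. A difference between arms with the same q is multiplied by (1 − q).

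The lowest q is a scale check. It spreads the plan's 25% example evenly over 84 days: −ln(0.75)/84 = 0.34% per day, or about 0.17% per half day. The last column starts from a 15-point difference (25% against an assumed 10%).

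| Assumed q | p′ when p = 25% | Extra subjects per 25 | 15-point difference becomes |
|---|---|---|---|
| 0.17% | 25.13% | 0.03 | 14.97 |
| 1% | 25.75% | 0.2 | 14.85 |
| 2% | 26.5% | 0.4 | 14.7 |
| 5% | 28.75% | 0.9 | 14.25 |
| 10% | 32.5% | 1.9 | 13.5 |

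For a single preferred term, q must refer to that term alone, so the rows with larger q are generous at that level.

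**The case against.** The strongest reply is that the SAP governs the detailed analysis (protocol section 17.2 lets it modify the protocol) and that its wording already excludes pre-dose events. It also plans to list baseline adverse events, so it recognises events outside the TEAE set. AE start time is collected, so the wording can be applied on the AE side. This stands to the extent that a reader who infers that pre-dose events definitely enter the primary endpoint goes beyond the documents.

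A reader might also infer from the SAP's imputation rules that the inclusive date rule is what will be programmed. Those rules are consistent with it, but they address only missing or partial dates. They do not settle how a complete date and time is handled.

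The effect is also modest. Nothing in the documents supports a q of several percent. Some Baseline procedures, including physical examination and laboratory tests, may be skipped when Screening falls within 5 days (protocol section 10.1.3.1). Pre-dose events cannot depend on treatment, and the planned AE analysis is within-arm incidence with confidence intervals. A material dilution of the OV101-placebo contrast is therefore not supported. The tables of treatment-related events rest on the investigator's causality assessment, which should screen out a pre-dose event. Finally, counting all first-day events can be a deliberate, inclusive safety convention.

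What the reply does not remove is the conflict. Neither document declares such a convention, and the protocol's words say the opposite. The published text of SAP section 3.11 lists no change to the TEAE definition, although the SAP's introduction undertakes to identify substantial differences from the protocol.

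**Conclusion.** The point holds as an unreconciled definition of the primary endpoint. Under the protocol's operational rule, a Day 1 event that starts before dosing is a TEAE. Under that rule's own words, and under the SAP, it is not. Neither document says how same-day events are to be resolved.

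The consequence is a possible slight inflation of within-arm incidence, about equal across randomized arms. In the scenarios above it runs from 0.13 to 7.5 points on a 25% incidence, and the upper end rests on a q that the documents do not support. Even 7.5 points is less than half the stated 17-point half-width. A difference between arms would shrink only by the factor (1 − q). The correction is worth making because it is cheap and concerns the primary endpoint, not because a large bias has been shown.

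**What to change.** Put the same rule in protocol section 16.1.1 and SAP section 3.9.1, and note the clarification in SAP section 3.11:

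> An AE that starts on the date of the first dose is treatment-emergent if it starts at or after the first dose, judged by the recorded AE start time and the first-dose time where available. If either time is missing, the AE is treatment-emergent unless it was recorded at the Baseline visit as starting before dosing.

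Keep the existing clause for events that begin before treatment and worsen afterwards. List Day 1 pre-dose AEs with the baseline adverse events already planned for the listings.

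The cost is a sentence in each document and a small change to the derivation. AE start time is already collected. No visible text says that the clock time of the first dose is recorded, so that time, or confirmation that the first dose was taken in the evening, must be available. Where it is not, the default stays inclusive. TEAE counts may be slightly lower than under the date rule.
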